#### 9.2.16.1.8 THERASPHERE ADMINISTRATION DOCUMENTATION

Any technical problems or complications related to the delivery of TheraSphere treatment to the patient must be documented in the medical record. The details of any event and its impact on the patient should be documented on an Adverse Event eCRF. Patients in the Treatment arm must certify continued eligibility prior to administration of TheraSphere. A new blood draw for labs and pregnancy and an ECOG Performance Status test may be performed within 7 days before TheraSphere administration at physician discretion to confirm baseline results.

Using institutional practices, the activity of each vial of TheraSphere will be determined prior to administration. This activity will be used to calculate the actual dose delivered to the liver and lung which will be recorded on the appropriate eCRF.

#### Calculation of the liver dose (Gy) delivered:

Calculation of the delivered dose per infusion takes into account the activity lost to lung shunting plus activity associated with residual microspheres in the administration system and is provided by the following formula:

> 50[Injected Activity (GBq)][1-F][1-R] Dose (Gy) = Mass of Selected Liver Target (kg)

where F = lung shunt fraction (determined in Section 9.2.14.1.3)

R = residual activity fraction

#### Calculation of residual activity fraction for microspheres:

The fraction of microspheres remaining in the device (R) is calculated using the following formula:

R = (W-b')/(I-b)

Where R = residual activity fraction

b = background dose rate prior to source vial measurement

I = measured dose rate of source vial positioned greater than 30 cm from ionization chamber (or other measuring device) and adjusted for radioactive decay to the time of waste measurement

b' = background dose rate prior to waste measurement

W = average dose rate of shielded waste container (containing discarded vial, microcatheter, tubing)

positioned with center in same location as I

#### Calculation of Actual Lung Radiation Exposure:

Calculation of the lung dose (Gy) delivered in each infusion is provided by the following formula:

Lung dose (Gy) = 50\* activity delivered (GBq)\*F

# 9.2.16.1.9 THERASPHERE POST-TREATMENT PATIENT MANAGEMENT

Immediately following treatment, the patient should remain under observation consistent with institutional standard of care guidelines for aftercare in procedures involving femoral or brachial artery catheterization. These aftercare guidelines are unique and subject to the policies and procedures dictated by the respective radiology and radiation safety departments at each institution. Prophylactic treatment using gastric inhibitor (H2 blocker or proton pump inhibitor) should continue for 14 - 21 days post treatment. In addition, steroids (e.g., Medrol Dose Pack) may be taken (with food) over the first six days post-treatment.

Prior to discharge, patients should be instructed regarding after-care and provided with a 24-hour telephone number that they may use to contact the Site Investigator if they develop a problem or have questions about their treatment.

Any concurrent medication or therapy deemed necessary, including gastric prophylaxis, to provide adequate supportive care to the patient in the immediate post-treatment period may be administered according to institutional standard of clinical care and should be documented on the Concurrent Medications eCRF.

#### 9.2.16.1.10 RADIATION SAFETY IN THE IMMEDIATE POST-TREATMENT PERIOD

Special radiation isolation procedures for Treatment arm patients are not necessary following TheraSphere Treatment. The existence of a small amount of long-lived radioactive byproducts in TheraSphere is a function of the production method. The predominant byproducts are Y-91, Y-88 and Cr-51 with respective half-lives of 59, 107 and 28 days. The 3 year accumulated dose to the patient's liver is estimated to be 1/1000 of the planned treatment dose.

Should a patient die or require surgery in the period immediately following-TheraSphere treatment the hospital radiation safety officer should be consulted. At 60 days after the TheraSphere calibration date, a surgeon explanting a treated liver in a procedure lasting one hour would be exposed to an estimated dose to the hands of <0.6 mrem. This is similar to estimated background doses from natural radiation sources which range from 0.5 to 0.8 mrem/day. Institutional radiation safety guidelines for handling of the body and/or body tissues should be followed.

#### 9.2.16.2 SOC SORAFENIB TREATMENT

Control arm patients will start SOC sorafenib therapy within 2 weeks after randomization.

All patients in the Control group will receive SOC treatment with sorafenib in accordance with the package insert. In accordance with the sorafenib package insert and country-specific policies, special attention should be paid to patients with hypertension or prolonged QT or at risk of developing QT prolongation (patients with a congenital long QT syndrome, patients treated with a high cumulative dose of anthracycline therapy, patients taking certain anti-arrhythmic medicines or other medicinal products that lead to QT prolongation, and those with electrolyte disturbances such as hypokalemia, hypocalcemia, or hypomagnesemia). In the United Kingdom, blood pressure monitoring plus electrocardiogram with magnesium and calcium laboratory tests done at screening and first post-therapy visit then every 6-8 weeks are recommended as SOC monitoring.

Abnormal results or adverse events related to these conditions observed in study subjects should be recorded as adverse events. Therapies used to manage such adverse events should be recorded in the Concomitant Medication eCRF.

Dosage adjustments and drug holidays will be determined to be in the patient's best interest at the discretion of the physician. In those countries where monitoring by ECG is required, consider discontinuing sorafenib if QT/QTc increases over 500ms or increases to 60ms above the baseline reading. All dosage adjustments must be logged on the Treatment Medication eCRF.

Caution is recommended when considering concomitant administration of the following medications; please consult the sorafenib summary of product characteristics for details:

- Warfarin, phemprocoumon or CYP2B6, CYP2C8 and CYP2C9 substrates (monitor regularly for changes in prothrombin time, INR or episodes of clinical bleeding)
- Inducers of metabolic enzymes such as rifampicin, St. John's wort, phenytoin, carbamezepione, phenobarbital, dexamethasone may increase sorafenib metabolism and decrease sorafenib concentrations
- UGT1A1 or UGT1A9 pathways metabolized compounds due to glucuronidation inhibition

#### 9.2.16.3 POST-PROGRESSION TREATMENT: BEST AVAILABLE CARE

All patients who meet the criteria for progression specified in Section 9.2.20 and received the treatments as described for either arm of the trial can receive institutional best available care. Patients in the control arm who have progressed are not allowed to cross-over to the treatment arm. Best available care is based on physician judgment and current standard of care practices, including sorafenib.

For patients in the control arm: In the case of recurrent unifocal lesion, resection or radiofrequency ablation are allowed providing the lesion(s) treated with sorafenib demonstrates tumor response (PR or CR) by RECIST v1.1. For any other progression, if resection or ablation is not appropriate, patients may receive best available care.

For patients in the treatment arm: In case of a previously treated tumor with progression per RECIST v 1.1 detected during follow up evaluations, re-treatment with TheraSphere is allowed if it does not exceed the maximum allowable three Y90 treatments. In the case of a treatable multifocal progression (ipsi or contralateral), a Y90 re-treatment is allowed if the lesion(s) treated with TheraSphere demonstrate tumor response (PR or CR) by RECIST v1.1, the lesion is amenable to TheraSphere treatment and the re-treatment procedure does not exceed the permited maximum three treatments.

## 9.2.17 Efficacy Imaging – CT/MRI

Baseline efficacy imaging scans will be obtained during screening and efficacy assessment scans will be taken every 8 weeks post randomization until progression is confirmed (see Section 9.2.20). Most patients will be evaluated by CT images. MRI images are also permitted. The imaging modality used at baseline must continue to be used for all efficacy images throughout the study. Triple phase CT will be used in accordance with site standards at baseline for dosimetry determination. SPECT imaging may be performed according to standard of care practices for clinical management but is not a study requirement.

Spiral CT abdomen/pelvis – must be performed with cuts of 10 mm or less in slice thickness contiguously in the axial plane. From these images, hepatic and extra-hepatic lesions will be read.

Spiral CT Chest – must be performed with cuts of 10 mm or less in slice thickness contiguously in the axial plane. From these images, extra-hepatic lesions will be read.

To enable analysis of secondary study endpoints using radiological assessment, investigators will identify, read and use bidimensional measurements of target lesions for size and will record evidence of enhancement and increase in dimension of a pre-existing thrombus for all image timepoints. These data will be captured on the eCRF. Comparison between baseline and subsequent images of quantitative and qualitative findings will determine response according to RECIST v 1.1, mRECIST and EASL which are assessed separately in secondary endpoint analyses.

Bone Scintigraphy – Bone scintigraphy to assess spread of metastatic disease will be performed according to institutional standards. For patients with AFP > 400 ng/mL at screening, results of bone scintigraphy will be recorded at the screening visit and subsequent study visits according to the site standard practice ( week 16 study visit and 6 months thereafter (i.e. months 10, 16, 22, etc.) ). Bone scintigraphy is suggested whenever there is an unjustified increase in AFP or the patient experiences bone pain or symptomatic deterioration and repeated at a frequency according to site standard practice.

#### 9.2.18 STUDY TREATMENT MEDICATION RECORD

The administration of study treatment will be recorded throughout the trial on the appropriate eCRF. Start/stop dates, dates of change of dosage, and any drug holidays will be recorded.

#### 9.2.19 CONCURRENT MEDICATION RECORD

At every study visit new or changes in concurrent medications will be documented on the appropriate concurrent medication eCRF. Documentation will include dosage, start/stop dates, date of change of dosage and any drug holidays.

Following determination of progression and receipt of treatment options in either arm of the study, record only medications used specifically for the treatment of HCC. Other medications do not need to be recorded.

#### 9.2.20 DEFINITION OF PROGRESSION FOR PATIENT MANAGEMENT DECISION-MAKING

For the purposes of this trial, definition of clinical progression for patient management decisions will include assessment of change in PVT status and tumor progression and is defined as:

- Radiological progression as defined by RECIST v 1.1 (after receiving all allowable TheraSphere treatments as specified by the protocol)
  - And/OR
- Development of extra-hepatic disease beyond the limits defined in the eligibility criteria
- Worsening of PVT from baseline defined as change in classification of PVT (per Shi et al) up to Type Illa; Type IIIb or Type IV may not be retreated
- ECOG Performance Status ≥2

#### 9.2.21 STUDY COMPLETION

Patients complete the trial upon reaching the primary efficacy endpoint of death.

#### 9.2.22 PATIENT WITHDRAWAL

A patient may decide he/she no longer wishes to participate in the trial. In accordance with the Declaration of Helsinki, and applicable state and federal regulations, a trial subject has the right to withdraw from the study at any time and for any reason. Every effort should be made to have patients complete the study within the provisions of informed consent. However, the participation of the patient may be discontinued at any time during the study when, in the judgment of the investigator, sponsor or subject, it is appropriate.

The reasons for study withdrawal include:

- Death of the patient
- Patient's desire for any reason to withdraw consent
- Administrative reasons (e.g. study termination)
- It is considered necessary by the investigator or sponsor, for any reason

Lost to follow-up is not an adequate reason for withdrawal. Patients should be encouraged to attend study visits until completion of the study or until a decision is taken to withdraw for one of the above-noted reasons.

If the patient is removed due to pregnancy or because of intolerance to the study treatment, he/she should be under medical supervision for as long as deemed appropriate by the treating physician. If the patient is discontinued due to an AE, the event will be followed until it resolves to the Investigator's satisfaction or is considered stable. The details and reasons for discontinuation must be carefully and completely documented.

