# 7 STUDY DESIGN

This is an open-label prospective, multi-center, randomized, controlled clinical trial that will evaluate the use of TheraSphere compared to standard-of-care sorafenib alone. Up to 25 study centers will participate and recruit patients for the protocol. Participating study sites may be in Europe, Asia or North America. All patients will be followed prospectively from randomization to death.

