#### 9.2.15 RANDOMIZATION (DAY 0)

According to an intention-to-treat (ITT) methodology, randomization will be performed upfront, before any further invasive tumor assessment (angiogram) or treatment planning.

Patients will be randomized 1:1 to study treatment, either the Control arm or the Treatment arm.

If a patient is determined to be eligible to participate in the trial, the study site will contact the central randomization office via telephone or by internet where randomization will be determined using assignment by a computer-generated randomization scheme. Upon randomization, each patient will be assigned a subject identity code consisting of the protocol number, the site number (e.g. 01) and a patient identifier number (e.g. 001).

In order to create a balance between study arms, patients will be stratified at randomization based on the following:

- AFP ≤ 400 ng/mL or >400 ng/mL
- Participating trial site

Although this will not be considered as stratification criteria upfront, each patient will be registered as naïve or recurrent, i.e. whether or not the HCC diagnosis presents at first diagnosis, with no previous treatment, or as a recurrent tumor.

Patients randomized to the Control arm or the Treatment arm, unable to receive their planned study treatment, will continue to be followed under their assigned study arm for the purpose of the intent-to-treat analysis.

Patients who do not meet the eligibility criteria should not be randomized and the reason for treatment ineligibility should be documented on the Screen Failure Log.

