#### 10.2.2 TRIAL ENDPOINTS

#### 10.2.2.1 PRIMARY EFFICACY ENDPOINT

The primary study endpoint is overall survival (OS) time, which will be calculated as the interval between the randomization date and the date of death for any cause, with censoring at the date of last contact for patients alive at last contact.

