6.4.1 Primary Efficacy Variable – Overall Survival (OS)

The primary study endpoint is OS defined as the time from date of randomization until date of death due to any cause. For each patient that is not known to have died, OS will be censored at the time of last contact date known to be alive (contacts considered in the determination of last contact date include adverse event start and end dates, lesion assessment date, and best available care start and end dates).

Overall Survival (months)= (Date of event/censor – Date of Randomization + 1)/30.4375.

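### Protocol 9.2.22 does not separate stopping treatment from leaving the study and requires no vital status after exit, so overall survival can be informatively censored

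*Protocol*

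**What the plan says.** **Removal.** Protocol 9.2.22 deals with withdrawal from the study. Besides the patient's own wish, its reasons include: "It is considered necessary by the investigator or sponsor, for any reason". It then speaks of patients removed for intolerance and patients discontinued because of an adverse event. For the first group it says: "If the patient is removed due to pregnancy or because of intolerance to the study treatment, he/she should be under medical supervision", with the duration left to the treating physician. For the second it says that "the event will be followed until it resolves to the Investigator's satisfaction or is considered stable". It does not mention survival status after either.

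**Exit.** Protocol 9.1.4 lists one-off activities at study exit (date and reason, ECOG, laboratory tests, treatments and adverse events, imaging, questionnaire) and no later contact. Protocol 12.3 records adverse events up to study exit. After that the investigator need not look for new ones, and reports a later serious event only on becoming aware of it and judging it at least possibly related.

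**Follow-up to death.** Protocol section 7 says: "All patients will be followed prospectively from randomization to death". Under 9.2.15, patients in either arm "unable to receive their planned study treatment, will continue to be followed under their assigned study arm". Under 9.2.21, a patient completes the trial by dying.

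**Analysis.** Protocol 10.2.2.1 defines OS "with censoring at the date of last contact for patients alive at last contact". SAP 6.4.1 says: "For each patient that is not known to have died, OS will be censored at the time of last contact date known to be alive". The contacts it lists are adverse event dates, lesion assessment dates and best-available-care dates; no survival contact or vital-status check is named.

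**The concern.** The log-rank test and the Cox model assume that, within an arm, a patient censored at a given time has the same later risk of death as one still followed. Someone removed for intolerance, for an adverse event, or on a physician's judgement in an open-label trial may well have a worse outlook than those who remain. If that patient's death is never recorded, the arm looks healthier than it was. If removal is more frequent in one arm, the hazard ratio is biased. The sample size allows for 5% of patients without a recorded death date, which covers lost events but does not protect against bias.

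**Working it through.** **1. The passages side by side**

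| Situation | What the protocol provides | Route to a death date |
|---|---|---|
| Stops treatment, stays on study, no progression yet | Visits every 4 weeks to week 24, then every 8 weeks (9.1.2.2, 9.1.3.3); not tied to being on treatment | Yes |
| After progression | Contact every 8 weeks until death (9.1.2.4, 9.1.3.5); the synopsis gives week 24 or progression as the starting point | Yes |
| Cannot receive the planned treatment | Followed under the assigned arm (9.2.15; SAP 4.2) | Yes |
| Removed or discontinued from the study (9.2.22) | Medical supervision, or follow-up of the event; one-off exit list (9.1.4) | None stated |

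Only the last row is a gap. A site that applied 9.2.22 literally would break no instruction in that section and could still lose the primary endpoint. The section also lists death as a reason for withdrawal, although 9.2.21 and SAP 8.1 count it as completion.

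**2. The plan's own figures**

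Inputs from protocol 10.1 and 10.2.3.1: medians 9 and 13 months (9/13 = 0.692), 250 deaths, analyses at 125, 188 and 250 deaths, rho = 1.5 spending, 320 patients, accrual A = 42 months, further follow-up F = 12 months, 5% without a death date.

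- Two-sided boundaries recompute to 0.0177, 0.0228 and 0.0322, as stated. Power at 250 deaths is 80.7% (HR 0.69) or 80.0% (HR 9/13).
- With exponential survival and uniform accrual, P(death) = 1 − [exp(−λF) − exp(−λ(A+F))]/(λA), where λ = ln 2/median. This gives 0.882 for control and 0.790 for TheraSphere, mean 0.836.
- 320 × 0.836 = about 268 deaths with complete follow-up, and × 0.95 = about 254 after the 5% allowance.

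The design figures are sound. The 254 is already net of the allowance, so deaths lost through removal must be counted from about 268.

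**3. What removal could do (every rate is an assumption)**

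Model A: 1,500 simulated trials of 320 patients per row, true HR 0.692, log-rank test at 0.0322, interim stopping ignored. Removed patients are censored 3 months before death, except in the row marked unrelated, where removal falls at random in months 0 to 6.

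| Removed, control / TheraSphere | Estimated HR | Deaths | Power |
|---|---|---|---|
| 0% / 0% | 0.69 | 267 | 82% |
| 5% / 5% | 0.69 | 254 | 81% |
| 10% / 2% | 0.74 | 251 | 61% |
| 20% / 5% | 0.79 | 233 | 36% |
| 2% / 10% | 0.65 | 252 | 91% |
| 10% / 2%, unrelated to prognosis | 0.69 | 254 | 79% |

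With a true HR of 1, the chance of a significant result favouring TheraSphere should be about 0.0322/2 = 1.6%. It is 0.8% at 10% / 2% and 5.8% at 2% / 10%.

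Model B: removal at 0.5 to 4 months, with the hazard raised only after removal. At 10% / 2% and a 1.5-fold hazard, the HR is 0.68 with full follow-up and 0.69 when censored. At 20% / 3% and a 2-fold hazard, it is 0.64 and 0.69.

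The shift therefore runs from nothing to about 0.10 (0.69 to 0.79), in either direction, depending on inputs the documents do not give.

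**The case against.** The best defence is that the protocol's intent is clear. Section 7 promises follow-up to death, 9.2.22 itself asks for every effort to keep patients to completion and rejects loss to follow-up as a withdrawal reason, and toxicity on sorafenib can be handled by dose adjustment or drug holidays. Protocol 10.2.5 reports discontinuation of active treatment separately from discontinuation of follow-up, and SAP 8.1 summarises reasons for study discontinuation by arm. The trial also stopped early (SAP section 5), so the 320-patient calculations are context only, and rewording 9.2.22 cannot undo past exits.

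Most of this stands, and it rules out three stronger readings:

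- A reader might infer that anyone who stops treatment loses survival follow-up. The visit schedules do not depend on treatment, and the synopsis provides 8-weekly visits to death.
- A reader might infer that the problem falls mainly on the sorafenib arm. Protocol 5.3 describes significant sorafenib toxicity, which makes this plausible, but no passage gives removal rates by arm.
- A reader might infer a known bias in favour of TheraSphere. If poor-prognosis sorafenib patients were removed more often, control survival would look too good and the bias would run against TheraSphere.

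The defence does not close the gap. A general promise in section 7 does not tell a site what to do after a formal removal. The protection in 9.2.15 reads most naturally as covering patients who cannot receive treatment at all; SAP 8.3.1 and 8.9 leave the never-treated out of the efficacy analysis, while those treated and later removed are in it.

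**Conclusion.** The point holds as an unreconciled conflict with a possible effect on the primary endpoint. Protocol 9.2.22 permits removal from the study with no later vital status, against sections 7, 9.2.15 and 9.2.21; OS for those patients is censored at last contact, and no sensitivity analysis addresses it. How many patients are affected, in which arm and with what prognosis cannot be learned from the documents, so neither the size nor the direction of the bias can be stated. The hazard ratios above are illustrations under assumed removal rates, timing and prognosis. The sample size and boundaries are not in error. Because the trial stopped early, the part that can still change the result is a vital-status check before database lock and its use in the OS analysis.

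**What to change.** 1. Reconcile protocol 9.2.22 with section 7 and 9.2.15: discontinuing treatment, or removal for any reason other than withdrawal of consent to follow-up, does not end survival follow-up. This concerns data collection only and leaves the treatment rules untouched.
2. Before database lock, check vital status for every randomised patient in both arms who is not known to be dead, including those already exited, from site records and, where permitted and consented, public registers.
3. In SAP 6.4.1, add the date of that check to the valid contacts for patients found alive. Deaths found enter as events.
4. Report reasons for OS censoring by arm. The discontinuation summary in SAP 8.1 comes close but is not linked to OS censoring.

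Cost: one clarifying paragraph, one SAP sentence, one data sweep before lock and a little extra reporting. Patients who have withdrawn consent to follow-up would remain censored.
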